## Research Question and Aims

**Aim 1: Evaluate the feasibility and acceptability of the AKI in Care Transitions pilot and iteratively refine the intervention.** Feasibility of the pilot will be quantified by the percentage of randomized AKI survivors who receive the full ACT intervention (nurse education visit, laboratory testing, pharmacist visit, primary care provider visit). Using encounter video recordings, and qualitative interviews with patients and clinicians, we will assess user interactions with the pilot intervention, tool fidelity, and acceptability of the intervention for patients and clinicians. Based on identified barriers and facilitators, the intervention will be iteratively refined for scaling and testing in a larger prospective clinical trial.

**Aim 2: Generate preliminary estimates of the ACT intervention on clinical and patient-reported outcomes.** We will conduct a pilot clinical trial in 50 patients over 18-months. Patients with severe AKI will be randomized 1:1 (25 per group) to either the control group (usual care) or the intervention group (ACT). In the intention-to-treat population, we will assess change in AKI knowledge from baseline to 30-days using a validated scale. Differences in other patient-reported and clinical outcomes will be characterized. The use of nephrotoxins will be quantified from reconciled medication lists. We *hypothesize* that the intervention group will experience improved AKI-related knowledge, processes of care, and outcomes compared to control patients.

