Randomization: Should the patient consent to participate, the individual will randomly be assigned 1:1 to one of two groups, the ACT group (intervention) or usual care (control). Randomization will occur via sealed envelopes which will contain the randomization information. Based on our preliminary data, randomization will be stratified according to hospital service/source: hospital medicine/family medicine or other services. Individuals will be randomly allocated equally to the intervention or control groups within each stratum using a permuted block design with varying block sizes of between 2 and 4. The target sample size is 50 (25 per group). The study coordinator will disclose the group allocation to patients after completing standard informed consent for participation in clinical research including permission to use protected health information.

Intervention: The ACT intervention was approved by the Mayo Midwest Clinical Practice Committee and local discipline specific subcommittees (nephrology, primary care, pharmacy). The intervention workflow was developed and pilot tested as part of IRB 20-004204. A description of the intervention is undergoing peer-review for publication ([name], et al.). As outlined in the preliminary data, patients randomized to the ACT intervention receive a multicomponent transitional support bundle including 1) a consultation from nurse educators before discharge to deliver kidney health education using approved materials available for use by any Mayo Clinic provider or patient (<http://intranet.mayo.edu/charlie/nephrology-hypertension-rst/education/patient/> , <https://askmayoexpert.mayoclinic.org/topic/clinical-answers/cnt-20114555/sec-20114604> ), 2) coordinated appointments for post-discharge laboratory testing (serum creatinine and urinalysis with microscopy), a primary care provider visit, and a pharmacist visit within approximately two weeks of discharge. Each of these elements would be considered standard for an AKI survivor, but the ACT intervention aims to operationalize them more cohesively and consistently to facilitate the care transition. A note will be entered into the patient's EHR to communicate enrollment to the healthcare providers. As an example, a note that may be entered for an intervention patient could be as follows:

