**Clinical and process outcomes:** Participants will be followed for 1 year post-discharge or until death or loss of follow-up within that timeframe. At 90-days, clinical outcomes to be assessed include Major Acute Kidney Event (MAKE) at 90-days, unplanned emergency department visit or rehospitalization. Incidence of de novo or progressive chronic kidney disease or death up to 12-months after discharge will be documented. Number of nephrotoxic medications, medication discrepancies, and drug therapy problems will be described. Process outcomes will include kidney laboratory assessments and their timing, clinician visits (e.g. with primary care provider, pharmacist, nephrologist), visit type (in-person vs telemedicine/virtual), and timing.

**Table 1.** Summary of study measures

Element	Source	Admission	Randomization	Discharge	Study follow-up visit (intervention patients only)	30-days	90-days	1-year
Sociodemographic factors, comorbidities	EHR	X						
Attributes of hospitalization and AKI episode	EHR			X				
Medication utilization	EHR	X		X		X		
Brief Health Literacy screen	Patient self-report		X					
mKiKS	Patient self-report		X			X		

PROMIS 10	Patient self-report		X			X		
Was it worth it?	Patient self-report					X a		
Encounter observation +/- video/audio recording	Direct observation					X a		
Qualitative interviews	Patient or clinician self report					X a		
MAKE, unplanned ED visit, rehospitalization	EHR						X	
CKD or death	EHR							X
Kidney laboratory assessments, outpatient clinician visits	EHR						X	

a: Intervention patients only

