### Statistical analysis

**Analysis plan:** To describe the feasibility of ACT and generate preliminary estimates of the effect on patient reported and clinical outcomes, descriptive analyses will be conducted in three groups 1) the intention to treat population (anyone randomized), 2) the per protocol population (randomized patients who receive the assigned study intervention; in the case of ACT patients this would include completion of nurse education, laboratory testing, pharmacist visit, and primary care provider visit), and 3) the complete follow-up population (the per protocol population with follow-up patient reported outcomes at 30 +/- 7 days). Baseline characteristics will be described with means and standard deviations and counts and percentages and compared using t-tests and chi-squared tests, respectively. Any baseline imbalances ( $p < 0.05$ ) will be explored as a possible factor to adjust for when the outcome measures are analyzed. The CONSORT guidelines will be followed to transparently report study results.

AKI knowledge will be described between groups with the mean mKiKS score. In patients with incomplete follow-up, model imputation will be used to impute follow-up scores. Mean between-group differences in the total baseline and follow-up scores will be compared using the t-test or non-parametric Mann Whitney U test. An exploratory multivariable linear regression model will be fit with group assignment as the independent predictor of interest, mean follow-up knowledge scores as the dependent variable, and baseline scores as a covariate. Other variables to be considered will include age, sex, baseline health literacy, socioeconomic status, and baseline comorbidities, specifically CKD. Clinical outcomes up to 12-months will be compared with Cox proportional hazards models.

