**Sample Size:** As a pilot clinical trial, we will include all eligible candidates during the enrollment period. Based on preliminary feasibility data, we estimate approximately 1-2 patients per week will be identified with the EHR trigger, of which 70% will be eligible, agree to participate in the trial, and have evaluable outcomes data. We, therefore, estimate enrollment of approximately 25 patients per group (50 total) during the 18-month study timeframe. A sample size of 25 participants per group would be sufficient to detect a mean difference of 2 points on the mKiKS score (12.5%), using a two-tailed alpha of 0.05 and 80% power, assuming a standard deviation of 15%. Results from this study will provide the necessary pilot data to inform future investigations.

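### A per-protocol Cox hazard ratio counted from discharge would favour ACT, because only ACT patients must complete post-discharge steps to enter that set; the Cox population and time origin should be stated

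*Combined protocol and SAP*

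**What the plan says.** All of this is in the combined protocol and SAP.

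- **Populations.** Under Statistical analysis, Analysis plan, the aim is to "generate preliminary estimates of the effect on patient reported and clinical outcomes, descriptive analyses will be conducted in three groups": intention to treat, per protocol, and complete follow-up (per-protocol patients who also have 30-day patient-reported outcomes).
- **Per-protocol rule.** Patients must have received their assigned intervention; "in the case of ACT patients this would include completion of nurse education, laboratory testing, pharmacist visit, and primary care provider visit". The rule sets no deadline.
- **Timing of the steps.** The Intervention paragraph places nurse education before discharge, then schedules laboratory testing, "a primary care provider visit, and a pharmacist visit within approximately two weeks of discharge".
- **Controls.** The Control paragraph gives them no study intervention, so they have no step to complete.
- **Model.** "Clinical outcomes up to 12-months will be compared with Cox proportional hazards models". The sentence gives no population, time origin, landmark or time-varying exposure.
- **Clock.** Under Outcomes, Clinical and process outcomes: "Participants will be followed for 1 year post-discharge or until death or loss of follow-up within that timeframe". MAKE, unplanned emergency visits and rehospitalization are assessed at 90 days; CKD or death up to 12 months.

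**The concern.** Per-protocol membership depends on what happens after discharge in one arm only. Suppose two patients die on day 4. The ACT patient has not finished the bundle, so the patient and the death both leave the per-protocol set. The control stays in and the death counts. Early readmission, an emergency visit or a dialysis start can act the same way if it stops the remaining visits. The Outcomes section foresees this, since it lists a change in goals of care or clinical status among the reasons for not completing ACT.

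A hazard ratio from discharge in that set therefore tends below 1 even if ACT does nothing. This is immortal-time bias. The pilot is meant to supply preliminary estimates for a larger trial, and the bias always points toward ACT, so a general caveat about small numbers would not disclose it.

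**Working it through.** **The plan's own figure.** The only sizing figure is for mKiKS: difference 12.5%, SD 15%, two-sided alpha 0.05, 80% power. n = 2 × (1.960 + 0.842)² × (15/12.5)² = 2 × 7.85 × 1.44 = 22.6, so 23 per group (24 with the t distribution). The stated 25 is adequate. It does not bear on the Cox models, for which no sizing is given.

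**Inputs for the check**
- One-year event risk 49%: the rehospitalization figure in Background and Significance, borrowed as an illustration.
- Completion day uniform on 2-10 or on 7-14 (assumed). Preliminary data gives the pilot pharmacist visit a median of 5 days (IQR 1-10) and describes a 7-14-day window.
- Weibull event times with shape k = 1 (constant hazard), 0.7 or 0.5 (front-loaded). The documents give no hazard shape, so this is assumed.
- Share of early events that block completion: all, or half (assumed).
- True hazard ratio 1; clock from discharge; all controls kept.

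**Step 1: hand approximation.** The Weibull cumulative hazard is proportional to t^k. If every event before completion day c is removed from ACT only, the hazard ratio to day H is roughly 1 − (c/H)^k. Using the mid-windows c = 6 and c = 10.5, with H = 90:
- k = 1: 1 − 6/90 = 0.93; 1 − 10.5/90 = 0.88.
- k = 0.5: 1 − √(6/90) = 0.74; 1 − √(10.5/90) = 0.66.

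**Step 2: simulation under the null, 90 days, large samples**

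| Hazard | All early events block | Half block |
|---|---|---|
| Constant | about 0.88-0.92 | up to about 0.96 |
| Strongly front-loaded (k = 0.5) | about 0.63-0.73 | down to about 0.82 |

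If completion is fixed at day 14 and every early event blocks, the 90-day ratio is 0.84 (k = 1), 0.70 (k = 0.7) and 0.58 (k = 0.5). On the same data, intention to treat and a day-14 landmark in both arms both return about 1.00.

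**Step 3: patients involved.** The share with an event by day 14 is 1 − 0.51^((14/365)^k).
- k = 1: 1 − 0.51^0.0384 = 0.0255, × 25 = 0.6 patients.
- k = 0.5: 1 − 0.51^0.196 = 0.124, × 25 = 3.1 patients.

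Earlier completion or partial blocking gives fewer, hence about 0-3 of 25.

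**Step 4: the 12-month outcome, CKD or death.** CKD is unlikely to be recorded in the first two weeks, so mainly early death matters. For an assumed 20% one-year risk, day-14 completion and full blocking, the 12-month ratio is 0.96 (k = 1), 0.89 (k = 0.7) and 0.80 (k = 0.5), with 0.2, 0.6 and 1.1 of 25 ACT patients removed. Later CKD events in the composite dilute this further.

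**Step 5: sampling error.** With D events split evenly, the 95% limits are about HR ×/÷ exp(1.96 × 2/√D).
- 12 months at 49%: D = 0.49 × 50 = 24.5, factor exp(3.92/4.95) = 2.2.
- 90 days, constant hazard: risk 1 − 0.51^(90/365) = 0.153, D = 7.7, factor exp(3.92/2.77) = 4.1.

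**Step 6: complete follow-up set.** This set requires the 30 ± 7-day survey in both arms, so early deaths leave both arms. Simulated for death, the ratio is about 1.00.

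**The case against.** The strongest reply is that no per-protocol Cox model is actually specified. The Cox sentence names no population, the three-group sentence speaks of descriptive analyses, and Aim 2 refers to the intention-to-treat population. This stands in part: the Cox population and the discharge origin are inferred. But the three-group sentence expressly covers effects on clinical outcomes, Cox is the only method named for comparing them, and the intention-to-treat phrase in Aim 2 is attached to the change in knowledge. An origin at randomization would lengthen the protected period, not remove it.

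Three stronger readings are tempting, and the documents do not support them.

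- **A reader might infer that ACT patients must be event-free until completion.** Only death strictly prevents completion. The per-protocol rule has no deadline, and the Intervention text keeps the care path active across inpatient and outpatient settings. A readmitted patient can still complete and stay in with the event.
- **A reader might infer that two of the three sets are equally affected.** In the complete follow-up set the survey requirement largely removes the asymmetry for death. It remains only for non-fatal events that block completion.
- **A reader might infer a substantial false benefit at 12 months.** Rehospitalization is a 90-day outcome in this plan, so 49% should not be carried over to the 12-month outcome. The low end of the 90-day range needs full blocking, strong front-loading and late completion together.

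It is also fair to say that hospice discharges and patients expected to need dialysis are excluded, which should lower early death and dialysis, and that all eight evaluable pilot patients completed the primary care visit and laboratory tests within two weeks.

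**Conclusion.** The point holds with limited weight. As written, the plan allows a per-protocol hazard ratio from discharge that is biased toward ACT, and nothing in the text prevents it. The bias matters mainly for the 90-day outcomes and for early death; it is expected to be small for 12-month CKD or death unless deaths cluster strongly in the first two weeks. The sizes above rest on an assumed event risk, hazard shape, completion time and blocking share; the direction was the same in every per-protocol scenario. In a trial of this size the bias is hidden within sampling error, and the planned intention-to-treat estimate is free of it. It is still worth correcting, because the error is systematic and the estimates are intended for planning.

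**What to change.** In the Analysis plan, state that Cox models for clinical outcomes are fitted in the intention-to-treat population, and name the time origin.

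If a per-protocol hazard ratio is kept, use a common landmark at day 14 after discharge. In both arms include only patients event-free at day 14, classify ACT completion as of that day, and count time and events from then. Label the result descriptive: the landmark removes the one-sided protected period, but completers remain self-selected.

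The cost is one or two sentences, with no new data or visits. The landmark estimate drops events in the first two weeks and is less precise.

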Pilot testing of each component of the ACT intervention began in April 2020 (IRB 20-004204). During the first phase of testing, the electronic health record indicator was optimized to identify candidate individuals for the ACT intervention. Alerts were manually validated and cross-referenced with clinical notes and nephrology service rosters. During the second phase of testing, the feasibility of the nurse education visit was evaluated. A nephrology nurse liaison successfully visited all 18 patients targeted for education. The nephrology consultation service, and by extension the nurse liaison, was not previously following 7 (39%) of these individuals. In the third testing phase, 11 individuals consented to participate and were placed on the AKI survivor care path. Of these individuals, one died before discharge, one was discharged on dialysis, and one did not receive education from the nurse liaisons before discharge. In the remaining eight patients, 100% completed an encounter with the PCP, a serum creatinine evaluation, and urinalysis within two weeks of discharge [median time to follow up 2 (IQR 1, 6) days]. Six (75%) completed an encounter with a pharmacist 5 (1, 10) days after discharge. Two (25%) patients consulted with an outpatient nephrologist on day one and day 22 after discharge, respectively. Over time, kidney health knowledge improved in the majority of patients. In the majority of patients who received education [from a nurse (phase 2) or a nurse + primary care provider +/- pharmacist (phase 3)], knowledge scores improved immediately after education delivery and remained improved for 2-4 weeks thereafter.

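### Does using 50 both as an evaluable count and as the number randomised leave the knowledge comparison underpowered?

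*Combined protocol and SAP*

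**What the plan says.** The Sample Size paragraph (Statistical analysis) starts from 1 to 2 patients identified per week, "of which 70% will be eligible, agree to participate in the trial, and have evaluable outcomes data", and concludes: "We, therefore, estimate enrollment of approximately 25 patients per group (50 total) during the 18-month study timeframe". It continues: "A sample size of 25 participants per group would be sufficient to detect a mean difference of 2 points on the mKiKS score (12.5"%), with two-tailed alpha 0.05, 80% power and a standard deviation of 15%.

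The number appears in two other places. Aim 2 says "We will conduct a pilot clinical trial in 50 patients over 18-months" and "Patients with severe AKI will be randomized 1:1 (25 per group"). The Randomization paragraph says "The target sample size is 50 (25 per group").

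The Analysis plan defines the intention-to-treat population as everyone randomised, provides for model imputation of missing follow-up scores, and defines a separate population with complete 30-day patient-reported outcomes. It gives no expected loss rate.

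**The concern.** A yield that includes evaluability produces a count of evaluable patients. Calling that count enrolment, and then using it as the number to randomise, is exact only if nobody is lost between randomisation in hospital and the knowledge score about 30 days after discharge.

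The plan itself foresees some loss, since it provides for imputation. The earlier pilot adds to the worry. Under Preliminary data: "In the third testing phase, 11 individuals consented to participate and were placed on the AKI survivor care path"; and then "Of these individuals, one died before discharge, one was discharged on dialysis".

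At stake would be the 80% power claim. A reader could take it as a property of 50 randomised patients when it belongs to 50 patients with scores, and a later trial could carry the figure forward with no allowance. The accrual sentence also looks loose: the stated rates over 18 calendar months give more than 50.

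**Working it through.** **Inputs (Sample Size paragraph).** Difference 2 points = 12.5%, so the scale has 2/0.125 = 16 points. SD 15% = 0.15 × 16 = 2.4 points. Standardised difference d = 2/2.4 = 12.5/15 = 0.833. Two-sided alpha 0.05, 25 per arm. The Analysis plan names the t-test or the Mann-Whitney test.

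**Reproducing the plan's figure.** Normal approximation: n per arm = 2 × (1.960 + 0.842)² / 0.833² = 22.6, so 23. The exact t-test (noncentral t with non-centrality d × √(n/2) and 2n − 2 degrees of freedom) needs 24. With 25 per arm, power is 82.3% by t-test and 83.8% by normal approximation. For Mann-Whitney with normal data (relative efficiency 0.955) it is 80.5%. The statement that 25 per group suffice is therefore correct.

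**Power if 30-day scores are missing (25 randomised per arm; all loss rates are assumptions).**

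| Loss | Analysed per arm | t-test | Normal approximation |
|---|---|---|---|
| 0% | 25 | 82.3% | 83.8% |
| 5% | 23.75 | 80.2% | 81.9% |
| 8% | 23 | 78.9% | 80.7% |
| 9.1% | 22.73 | 78.4% | 80.2% |
| 10% | 22.5 | 78.0% | 79.8% |
| 20% | 20 | 72.9% | 75.0% |

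Mann-Whitney at 10% loss gives 76.0%. The t-test difference detectable with 80% power is 1.94 points at 25 per arm, 2.03 at 23 and 2.18 at 20.

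**Where 9.1% comes from.** One of 11 pilot patients died before discharge: 1/11 = 9.1%, exact 95% interval 0.2% to 41%. This is one event, and it does not measure 30-day non-response. The pilot patient discharged on dialysis is not a guide either, because this trial excludes people expected to need dialysis at discharge.

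**What the planned analysis gives back.** With regression imputation from baseline, the variance of an arm mean is proportional to ρ²/25 + (1 − ρ²)/m, with m scores observed. For an assumed ρ = 0.5 and m = 23: 0.25/25 + 0.75/23 = 0.0426, an effective n of 23.5 and power of 79.8%. At m = 20 the effective n is 21.1 and power 75.1%. So imputation recovers part of the loss. The exploratory baseline-adjusted regression uses d/√(1 − ρ²). With an assumed ρ of only 0.3, power at 10% loss is 81.7%.

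**Accrual.** Over all 18 months (78 weeks): 78 × 1 × 0.70 = 54.6 and 78 × 2 × 0.70 = 109.2. At one per week over 72 weeks: 72 × 0.70 = 50.4. The paragraph distinguishes an enrolment period from the 18-month timeframe and gives no length for the former. If recruitment lasted 12 months (an assumption), 50 would need 50/(52 × 0.70) = 1.37 identified per week, inside the stated range of 1 to 2. The 50 does not contradict its inputs.

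**The case for a change.** The case for a change is that the two uses of 50 agree only at zero loss, and that the margin is thin: 25 per arm against a minimum of 24. The unadjusted t-test falls below 80% at a little over 5% loss. Imputation restores only part of the information, and the stated power does not rest on the adjusted model, which the plan labels exploratory. One feasibility measure is the number randomised, so a reader may fairly ask whether 50 means randomised or evaluable. Two sentences would settle it at no cost in patients or visits.

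The ambiguity stands: the Sample Size paragraph uses enrolment for a count that its own yield makes evaluable. The t-test figures stand too. But the Aims and the Randomization paragraph already say that 50 are to be randomised, so the suggested clarification would mostly repeat them. The rest would be a sensitivity calculation on loss rates that the documents do not supply. The worry about later trials is speculative, because the protocol says that the results, not this calculation, will inform future work.

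**Conclusion.** No change is needed. No stated number is wrong: 25 per arm give 82% power by t-test against a claimed 80%, and the 50 is compatible with the accrual inputs because the length of the enrolment period is not given.

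The possible shortfall is 1 to 2 percentage points at an assumed 8% to 10% loss. It is close to nil under the normal approximation (80.7% at 8%, 79.8% at 10%). At an assumed 20% loss, t-test power would be 73%, or about 75% after imputation with ρ = 0.5; nothing in the documents establishes a loss that large.

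The consequence is also slight. Feasibility is Aim 1, the Analysis plan describes its analyses as descriptive with preliminary effect estimates, and no decision depends on reaching 80% power. The populations, imputation and tests would be the same whichever meaning of 50 is intended. An analyst would report how many were randomised and how many had scores, and the confidence interval would reflect the precision achieved. This is loose wording that a reader can resolve from the rest of the document.
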